APPENDIX H: LIST OF ABBREVIATIONS AND DEFINITIONS OF TERMS

AAT	Alpha-1 Antitrypsin
ABW	Actual Body Weight
ADA	Anti-Drug-Antibody
AE	Adverse Event
AIBW	Adjusted Ideal Body Weight
Allo-HSCT	Allogeneic Hematopoietic Stem Cell Transplantation
ATG	Anti-Thymocyte Globulin
AUC	Areas Under the Time-Concentration Curves
B-cells	B Lymphocytes
BAT	Best Available Therapy
BSA	Body Surface Area
BMI	Body Mass Index
Cmax	Peak Concentration
CBC	Complete Blood Count
CD3/TCR	CD3 T-Cell Receptor
CI	Confidence Interval
CIBMTR	Center for International Blood and Marrow Transplant Research
CK	Creatine Kinase
CLL	Chronic Lymphocytic Leukemia
CLS	Capillary Leak Syndrome
CMV	Cytomegalovirus
CNI	Calcineurin Inhibitor
CR	Complete Response, the disappearance of symptoms in all organ systems
CRA	Clinical Research Associate
CRO	Clinical Research Organization
CRS	Cytokine Release Syndrome
CTCAE	Common Terminology Criteria for Adverse Events
eCRFs	electronic Case Report Forms
CTCAE	Common Terminology Criteria for Adverse Events
DoCR	Duration of Complete Response
DRI	Disease Risk Index
DSMB	Data and Safety Monitoring Board
EBV	Epstein-Barr Virus
EDC	Electronic Data Capture
ERC	Endpoint Review Committee
FDG	Fluoro-deoxyglucose
GCP	Good Clinical Practice
GI	Gastro-intestinal
GVHD	Graft-Versus-Host Disease
aGVHD	(acute) Graft-Versus-Host Disease
cGVHD	(chronic) Graft-Versus-Host Disease

List of Abbreviations and Definitions of Terms

SR-aGVHD	Steroid-refractory (acute) Graft-Versus-Host Disease
HCT	Hematopoietic Cell Transplantation
IBW	Ideal Body Weight
ICF	Informed Consent Form
ICH	International Conference on Harmonization
IEC	Institutional Ethics Committee
IFN	Interferon
Ig	Immunoglobulin
IL	Interleukin
IRB	Institutional Review Board
ITT	Intention-To-Treat
JAK	Janus Kinase
mAb	Monoclonal Antibody
MMF	Mycophenolate Mofetil
MOP	Manual of Procedures
MTX	Methotrexate
NIH	National Institutes of Health (USA)
NK cells	Natural Killer Cells
NR	Non-Responder; No Response, Progression/Relapse of aGVHD or death by the end of Day 28
NRM	Non-Relapse Mortality
ORR	Overall Response Rate
OS	Overall Survival
PBMC	Peripheral Blood Mononuclear Cells
PD	Progressive Disease, progression in 1 or more organ-systems resulting in a worsening of overall at least one Grade, without improvement in any other organs
PET	Positron Emission Tomography
PHA	Phytohemagglutinin
PI	Principal Investigator
PK	Pharmacokinetics
PP	Per Protocol
PR	Partial Response, the improvement of 1 or more organs, with no worsening in other organs
PRO	Patient Reported Outcomes
Progression/Malignancy Relapse	The time from the date of the start of treatment to the date of hematologic malignancy relapse/progression.
REG3 α	Regenerating Family Member 3 Alpha
RFS	Relapse Free Survival
RTA	Ricin Toxin A-chain
SAE	Serious Adverse Event
SCTOD	Stem Cell Transplant Outcomes Database
SoC	Standard of Care
SOS/VOD	Sinusoidal obstruction syndrome/veno-occlusive disease

List of Abbreviations and Definitions of Terms

SPRT	Sequential Probability Ratio Test
SPV-T3a	Anti-CD3, IgG2b
SR	Steroid-refractory
ST2	Interleukin 1 receptor-like 1
$t_{1/2}$	Terminal-phase Elimination Half-life
T cells	T Lymphocytes
TCR	T-cell Receptor
TEAE	Treatment Emergent Adverse Event
TMA	Thrombotic Microangiopathy
WT1	Anti-CD7, IgG2a
3-IS	3-Indoxyl Sulfate

APPENDIX K: SCHEDULE OF ASSESSMENTS
Table K-1: Required Assessments for T-Guard Arm

Assessment	Prior to Randomization	Day of Randomization and Prior to Treatment	First Infusion	Second Infusion	Third Infusion	Fourth Infusion	Follow-up							
							6	14	21	28*	35	42	49	56
Target study day	-1	0	0	2	4	6								
Window (days)	-3 to -1	0	0 to 3	2 post-previous infusion	2 post-previous infusion	2 post-previous infusion	+/-3	+/-3	+/-3	+/-3	+/-3	+/-3	+/-3	+/-7
Study drug administration			X	X	X	X								
Acute GVHD evaluation, including bilirubin	X	X	X ²	X	X	X								
Chronic GVHD evaluation														
Medical History	X													
Physical exam (weight and height)		X												
Vital signs (temperature, pulse, respiratory rate) ⁴			X	X	X	X								
Blood pressure			X	X	X	X								
CBC with differential and platelet count	X	X	X ²	X	X	X								
Albumin	X		X	X	X	X								
Renal function (blood urea and/or blood urea nitrogen, Creatinine)	X							X	X	X				
Schistocytes, haptoglobin and LDH	X							X	X	X				
CK levels ⁵	X													
Peripheral blood for CMV and EBV viral load								X	X	X	X	X	X	X
Pregnancy test (if applicable) ⁶	X													
Karnofsky performance status			X								X			
Pharmacokinetics ^{7, 8}			X	X	X	X					X	X		
Peripheral blood for Anti-Drug Antibody ^{7, 9}		X						X	X	X			X	X

Assessment	Prior to Randomization	Day of Randomization and Prior to Treatment	First Infusion	Second Infusion	Third Infusion	Fourth Infusion	Follow-up							
							6	14	21	28*	35	42	49	56
Target study day	-1	0	0	2	4	6								
Window (days)	-3 to -1	0	0 to 3	2 post-previous infusion	2 post-previous infusion	2 post-previous infusion	+/-3	+/-3	+/-3	+/-3	+/-3	+/-3	+/-3	+/-7
Peripheral blood for GVHD biomarkers REG3α and ST2 ⁷		X				X	X	X	X					+/-7
Peripheral blood mononuclear cells (PBMC) ⁷		X					X	X	X					
Peripheral blood for immunophenotyping ⁷		X					X	X	X					X
Urine sample for GVHD biomarker 3- S ⁷		X					X	X	X					X
Concomitant medication review ¹⁰	X	X	X	X	X	X	X	X	X	X	X	X	X	X
AE/SAE assessment ¹¹		X	X	X	X	X	X	X	X	X	X	X	X	X
Toxicity assessment											X	X	X	X
Patient-reported outcomes: PROMIS			X							X			X	X
Infection monitoring														
Primary disease relapse reporting														

¹Participants will be followed for survival post Day 180

²Assessment does not need to be repeated if treatment starts on same day as randomization

³Patients will be instructed to contact the site when their aGVHD symptoms worsen in between visits Day 70, 90 and 180

⁴Visual signs should be taken directly pre-infusion, 15 minutes after the start of the infusion, then every 30 minutes during the infusion, and at 1-hour post-infusion. Deviation of +/- 5 minutes may occur for all vital sign collection timepoints.

⁵If patients experience muscle pain, then a serum CK should be performed

⁶May be performed within 30 days of enrollment

⁷Research-specific samples must be drawn after participant signs consent, see [APPENDIX B](#) for more details

⁸Pharmacokinetic blood samples for T-Guard participants only. Samples directly at pre-infusion and at 4, 5, 6, 8, and 24 hours after start of 1st infusion; pre-infusion and at 4 and 24 hours after the 2nd and 3rd infusion; and pre-infusion and at 4, 6, 24 and 48 hours after the 4th T-Guard infusion. A window of +/- 15 minutes is allowed for samples drawn at 4 hours after the start of infusion, a window of +/- 30 minutes for the sample drawn 5, 6, and 8 hours after the start of infusion, and a window of +/- 1 hour for samples drawn 24 and 48 hours after the start of infusion. Every effort should be made to collect PK samples at all timepoints; however, **no** PK sampling is required on weekend days.

⁹Blood sample for ADA assessment should be collected for participants in the T-Guard treatment arm only. Day 6 sample should be collected just prior to the 4th dose infusion. All concomitant medications other than immunosuppressant agents will be collected starting at 7 days prior to randomization through 30 days after last dose of T-Guard. For all immunosuppressant agents, the overall start and stop date will be captured. For agents where dosing is tapered in response to drug levels, the medication dosing will not require reporting. Dosing for corticosteroids will be captured for all dosing changes.

¹⁰AEs and SAEs will be reported as described in Section [4.4](#) Adverse Event Reporting

¹¹In the case where T-Guard was started 2 or 3 days after randomization, the Day 28 visit should be scheduled on either Day 29 or 30. If this scheduling is not possible, the Day 28 post-randomization visit should still be completed within the allotted window and a separate visit should be arranged at Day 28 +/- 2 days post T-Guard initiation to collect aGVHD and systemic immunosuppression assessments.

Table K-2: Required Assessments for Ruxolitinib Arm

Assessment	Prior to Randomization	Day of Randomization and Prior to Treatment	Treatment and Follow-up									
			0	6	14	21	28	35	42	49	56	70
Target study day	-1	0	0	0	6	14	21	28	35	42	49	56
Window (days)	-3 to -1	0	0 to 3	+/-3	+/-3	+/-3	+/-2	+/-3	+/-3	+/-3	+/-3	+/-7
Study drug initiation ²		X										
Acute GVHD evaluation, including bilirubin	X	X	X ³	X	X	X	X	X	X	X	X ⁴	X ⁴
Chronic GVHD evaluation							X			X		X
Medical History	X											
Physical exam (weight and height)		X										
Blood pressure		X	X	X	X	X	X	X	X	X	X	X
CBC with differential and platelet count	X	X	X ³	X	X	X	X	X	X	X	X	X
Albumin	X		X	X	X	X	X	X	X	X	X	X
Renal function (blood urea and/or blood urea nitrogen, Creatinine)	X		X	X	X	X	X	X	X	X	X	X
Schistocytes, haptoglobin and LDH	X		X	X	X	X	X	X	X	X	X	X
CK levels ⁵	X											
Peripheral blood for CMV and EBV viral load		X	X	X	X	X	X	X	X	X	X	X
Pregnancy test (if applicable) ⁶	X											
Karnofsky performance status	X						X				X	X
Peripheral blood for GVHD biomarkers REG3 α and ST2 7	X		X	X	X	X	X					
Peripheral blood mononuclear cells (PBMC) 7	X			X	X	X	X			X	X	X
Peripheral blood for immunophenotyping 7	X			X	X	X	X			X	X	X
Urine sample for GVHD biomarker 3-IS 7	X	X	X	X	X	X	X					
Concomitant medication review ⁸	X	X	X	X	X	X	X	X	X	X	X	X
AE/SAE assessment ⁹		X	X	X	X	X	X	X	X	X	X	X
Toxicity assessment									X	X	X	X
Patient-reported outcomes: PROMIS		X							X	X	X	X

Assessment	Prior to Randomization	Day of Randomization and Prior to Treatment	Treatment and Follow-up											
			0	6	14	21	28	35	42	49	56	70	90	180 ¹
Target study day	-1	0	0	6	14	21	28	35	42	49	56	70	90	180 ¹
Window (days)	-3 to -1	0	0 to 3	+/-3	+/-3	+/-2	+/-3	+/-3	+/-3	+/-3	+/-3	+/-7	+/-7	+/-7
Infection monitoring			Reporting of infections at time of occurrence from time of enrollment through Day 180											
Primary disease relapse reporting			Reporting of relapse at time of occurrence from time of enrollment through Day 180											

¹Participants will be followed for survival post Day 180

²Refer to the pharmacy manual for details of ruxolitinib schedule

³Assessment does not need to be repeated if treatment starts on same day as randomization

⁴Patients will be instructed to contact the site when their aGVHD symptoms worsen in between visits Day 70, 90 and 180

⁵If patients experience muscle pain, then a serum CK should be performed

⁶May be performed within 30 days of enrollment

⁷Research-specific samples must be drawn after participant signs consent, see [APPENDIX B](#) for more details

⁸All concomitant medications other than immunosuppressant agents will be collected starting at 7 days prior to randomization through Day 44. For all immunosuppressant agents, the overall start and stop date will be captured. For agents where dosing is tapered in response to drug levels, the medication dosing will not require reporting. Dosing for corticosteroids will be captured for all dosing changes.

⁹AEs and SAEs will be reported as described in Section [4.4](#) Adverse Event Reporting

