2.5 TREATMENT PLAN

Participants should start treatment as close to the time of randomization as possible but no later than 72 hours after randomization.

Figure 2-1: Treatment Schema

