3.3 PRIMARY ENDPOINT

The primary endpoint is the proportion of participants with a CR on Day 28 after randomization.

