4.3 STUDY MONITORING

4.3.1 Follow-up Schedule

The Follow-up Schedule for scheduled study visits is outlined in [Table 4-1](#).

The timing of follow-up visits is based on the date of randomization (Day 0). A detailed description of each of the forms and the procedures required for forms completion and submission can be found in the Data Management Handbook and User's Guide.

Table 4-1: Follow-up Schedule

Assessment Time	Target Day (Days Post- Randomization)
1 week	6 days ¹
2 weeks	14 days ²
3 weeks	21 days ²
4 weeks	28 days [#]
5 weeks	35 days ²
6 weeks	42 days ²
7 weeks	49 days ²
8 weeks	56 days ²
10 weeks	70 days ³
90 days	90 days ³
6 months	180 days ⁴

¹Target day window for Ruxolitinib arm only is +/-3 days (see section [2.5.1.5](#) for guidance on T-Guard infusion delays)

²Target day window is +/- 3 days

³Target window is +/-14 days

⁴Target window is +/-28 days

[#]Target day window is +/-2 days

Data Collection: The investigator or site designee will enter data collected using an electronic data capture system. In the interest of collecting data in the most efficient manner, the investigator or site designee should transcribe data (including laboratory values, if applicable) in the eCRF in a timely manner after the participant visit unless otherwise noted. The BMT CTN DCC will be reviewing form submission regularly and will follow-up to assure data is submitted promptly.

The investigator or site designee is responsible for ensuring that all data in the eCRFs and queries are accurate and complete and that all entries are verifiable with source documents. These documents should be appropriately maintained by the site.

The monitor will verify a subset of the data in the eCRFs with source documents and confirm that there are no inconsistencies between them.

Criteria for Forms Submission: Criteria for timeliness of submission for all study forms are detailed in the Data Management Handbook and User's Guide. Forms that are not entered in the EDC system within the specified time will be considered delinquent. Transplant Centers can view past due forms via the EDC system. A missing form will continue to appear until the form is entered into the EDC system, or until an exception is granted and entered into the Missing Form Exception File, as detailed in the Data Management Handbook and User's Guide.

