The pivotal analysis for this study involves comparison of the Day 28 CR rate between arms in the primary (ITT) analysis population. The summary measure used to compare Day 28 CR rates between T-Guard and Ruxolitinib is the odds ratio, to be evaluated using logistic regression while adjusting for region (US vs. Europe) and age (at least 55 years vs. under 55) and acute GVHD grade at randomization (Grade III vs. IV). Testing will be one-sided at an overall significance level of 0.025. Two efficacy analyses for the primary endpoint will be performed as described in Section 5.2.2, one interim and one final, with the O'Brien-Fleming error spending function used to determine the appropriate critical values for each analysis.

The Day 28 CR rate will be described for each arm using the sample proportions and corresponding 95% confidence intervals.

A secondary analysis will assess the proportions of treated participants who attain a CR at Day 28 post-treatment initiation. This set of participants will include those from the PP population who are not in CR at the time of treatment initiation, with symptoms compared from the time of initiation to 28 days following initiation to determine CR status. This Day 28 CR rate will be described for each arm using the sample proportions and corresponding 95% confidence intervals. Day 28 CR rates will be compared between T-Guard and ruxolitinib using logistic regression while adjusting for region (US vs. Europe) and age (at least 55 years vs. under 55) and acute GVHD grade at randomization (Grade III vs. IV).

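### Late starters on T-Guard are directed to a Day 29 or 30 visit for the Day 28 primary endpoint; late starters on ruxolitinib are not

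*Combined protocol and SAP*

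**What the plan says.** - Section 3.3: "The primary endpoint is the proportion of participants with a CR on Day 28 after randomization". Section 4.3.1 counts visits in both arms from randomization, and the Table 4-1 footnote for Day 28 reads "Target day window is +/-2 days", that is, Days 26 to 30.
- Section 2.5 requires treatment in either arm to begin "no later than 72 hours after randomization"; section 4.2.1 repeats the limit and prefers a start within 24 hours.
- Appendix K, last footnote under Table K-1 (T-Guard): "where T-Guard was started 2 or 3 days after randomization, the Day 28 visit should be scheduled on either Day 29 or 30". If that cannot be arranged, the participant keeps the ordinary in-window visit and has one more: "a separate visit should be arranged at Day 28 +/- 2 days post T-Guard initiation". The extra visit records aGVHD and systemic immunosuppression.
- Appendix K, Table K-2 (ruxolitinib): none of its nine footnotes covers a late start. The one on drug initiation only points to the pharmacy manual.
- Section 5.2.1: the single-arm FDA analysis is timed from T-Guard initiation, which is the apparent reason for the K-1 footnote.
- Section 5.5: "A secondary analysis will assess the proportions of treated participants who attain a CR at Day 28 post-treatment initiation". That analysis is compared between arms by logistic regression.

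**The concern.** Two participants who both start on Day 3, one per arm, have different target dates for the same randomized endpoint. The T-Guard participant is directed to Day 29 or 30, the ruxolitinib participant to Day 28. A visit window is meant to absorb undirected scatter; here one arm is steered into its later half because of a need that belongs to a separate single-arm analysis. CR is a status on a given day, so the assessment date is part of the endpoint definition. The endpoint supports the EMA application, and the trial is open-label.

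The section 5.5 comparison timed from treatment start has the opposite gap. T-Guard late starters have a visit rule designed for it and ruxolitinib late starters have none.

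**Working it through.** **1. Days since initiation at each possible visit** (visit day minus start day)

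| Start | Visit Day 28 | Visit Day 29 | Visit Day 30 | Day 28 ±2 after initiation, in study days |
|---|---|---|---|---|
| Day 2 | 26 | 27 | 28 | 28 to 32 |
| Day 3 | 25 | 26 | 27 | 29 to 33 |

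- The K-1 footnote moves the target by 1 or 2 days (mean 1.5). The shift for ruxolitinib is 0.
- A Day 2 starter seen on Day 28 is already within two days of post-initiation Day 28. A Day 3 starter seen on Day 28 is at Day 25, outside it. Only Day 3 starters therefore need a different date if seen on Day 28 itself.
- Under the fallback, the separate T-Guard visit can overlap the Day 26-30 window (Days 28-30 for a Day 2 start, Days 29-30 for a Day 3 start). Section 5.5 has no rule for choosing between two in-window assessments.

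**2. The plan's own operating characteristics.** Inputs: 43% vs 26%, 123 per arm, looks at 150 and 246 with Z boundaries 2.6562 and 1.9817 (Table 5-2), and futility at 4 or fewer CRs in 23 (Table 5-1). A fixed design at one-sided 2.5% and 80% power needs 122 per arm, or 244, against 246 stated. Simulation with an unadjusted Z (4 million runs, futility followed):

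| | Table 5-2 | Unpooled Z | Pooled Z |
|---|---|---|---|
| Power | 80.56% | 80.5% | 79.9% |
| Interim power | 34.14% | 34.1% | 32.3% |
| Type I error (both rates 26%) | 2.37% | 2.41% | 2.32% |

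Table 5-2 rests on 100,000 runs. Its Monte Carlo standard error is √(0.0237 × 0.9763 / 100,000) ≈ 0.05 points, so the design is reproduced. The sample size is not in dispute.

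**3. Size of the shift.** The documents give neither the late-start share nor the daily CR gain, so both are assumed.
- Daily gain consistent with the null: 26% / 28 = 0.93 points per day (linear net accrual).
- Shift in T-Guard CR rate = late share × 1.5 days × 0.93.
- 10% late: 0.10 × 1.5 × 0.93 = 0.14 points. 40% late: 0.40 × 1.5 × 0.93 = 0.56 points.

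**4. Effect on one-sided type I error** (true rates equal at 26%, futility followed)

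| T-Guard shift | Pooled Z | Unpooled Z |
|---|---|---|
| 0 | 2.32% | 2.41% |
| 0.14 points | 2.46% | 2.55% |
| 0.56 points | 2.92% | 3.02% |

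**5. Ruxolitinib and the post-initiation analysis.** Section 4.3.2 requires aGVHD staging at Days 28 and 35 in both arms, with windows of Days 26-30 and 32-38. A Day 3 ruxolitinib starter needs an assessment on Days 29-33. One may fall on Days 29-30 or 32-33, but nothing directs it there and nothing says which visit to use.

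**The case against.** The strongest reply is that little actually changes. Only T-Guard participants starting on Day 2 or 3 are affected, and the plan prefers a start within 24 hours. Days 29 and 30 are open to both arms, the wording is advisory, and a fallback exists. No shifted visit falls more than 28 days after initiation. All of this stands and limits the size. It does not remove the asymmetry: the shift is the default for one arm, and the endpoint counts from randomization.

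The direction can also be challenged. Extra days allow more time to reach CR, but also more time for flare, new therapy or death. That stands in part. On a literal reading, section 5.5 counts added systemic therapy only through Day 28 while staging would come from the later visit, which tilts the balance toward T-Guard without proving it.

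Blinded adjudication of Day 28 response (section 3.6) answers part of the open-label concern, but it works from the submitted data and cannot correct the assessment date.

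A reader might infer that the two arms as a whole are assessed at different times, or that T-Guard gains a demonstrated advantage. The documents support neither: the rule covers a subset and stays within a common window. A reader might also take the daily gain from the 43% rate (43%/28 ≈ 1.5 points), giving 0.40 × 1.5 × 1.5 = 0.9 points and type I error of 3.3-3.5%. That mixes the alternative's accrual rate with a null of 26% in both arms. Nor does the ruxolitinib arm necessarily lack post-initiation data, since its Day 28 and Day 35 visits can supply some. What is missing is a rule.

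**Conclusion.** The schedule sets an arm-dependent target date for the randomized primary endpoint among late starters, inside a shared window, and leaves the section 5.5 post-initiation comparison without a matching ruxolitinib visit rule. The likely direction favors T-Guard but is not certain.

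Under the stated assumptions the inflation is 0.14 to 0.56 points, and one-sided type I error rises from 2.3-2.4% to about 2.5-3.0%. These figures are illustrative. They depend on an assumed late-start share, linear net accrual of CR, an unadjusted test and the futility rule being followed. No large effect is shown, so treating this as a defect that must be fixed would go beyond the documents. It is a moderate-to-low point, worth correcting because it touches the pivotal endpoint and is cheap to remove.

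**What to change.** Apply one late-starter visit rule in both arms.

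- Preferred: in Tables K-1 and K-2, target the primary assessment at Day 28 after randomization, ±2 days. Under both tables, add the separate aGVHD and systemic immunosuppression assessment at Day 28 ±2 after initiation, for late starters whose Day 28 visit does not already fall in that window.
- Minimum: copy the K-1 footnote to K-2, worded for ruxolitinib.
- In section 5.5, state that the in-window assessment closest to Day 28 after randomization feeds the primary endpoint, and that the one closest to Day 28 after initiation feeds the post-initiation analyses.

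Cost: edits to two footnotes, one added rule in 5.5, and one short extra assessment for some late starters, of a kind the plan already foresees for T-Guard. Sample size and boundaries are unchanged.
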